13.4.3 Evaluation of Best Overall Response

The best overall response is the best response recorded from the start of the treatment until disease progression/recurrence (taking as reference for progressive disease the smallest measurements recorded since the treatment started). The participant's best response assignment will depend on the achievement of both measurement and confirmation criteria.

Table 13.3 For Participants with Measurable Disease

Target Lesions	Non-Target Lesions	New Lesions	Overall Response	Best Overall Response when Confirmation is Required*
CR	CR	No	CR	≥4 wks. Confirmation**
CR	Non-CR/Non-PD	No	PR	≥4 wks. Confirmation**
CR	Not evaluated	No	PR	
PR	Non-CR/Non-PD/not evaluated	No	PR	documented at least once ≥4 wks. from baseline**
SD	Non-CR/Non-PD/not evaluated	No	SD	
PD	Any	Yes or No	PD	no prior SD, PR or CR
Any	PD***	Yes or No	PD	
Any	Any	Yes	PD	

*** In exceptional circumstances, unequivocal progression in non-target lesions may be accepted as disease progression.

Note: Participants with a global deterioration of health status requiring discontinuation of treatment without objective evidence of disease progression at that time should be reported as “symptomatic deterioration.” Every effort should be made to document the objective progression even after discontinuation of treatment.

13.4 For patients with only non-enhancing lesions, the low-grade glioma RANO criteria will be used.

Complete response Complete response requires all the following criteria compared with the baseline scan: (1) Complete disappearance of the lesion on T2 or FLAIR imaging (if enhancement had been present, it must have resolved completely); (2) no new lesions, no new T2 or FLAIR abnormalities apart from those consistent with radiation effects, and no new or increased enhancement; (3) patients must be off corticosteroids or only on physiological replacement doses; and (4) patients should be stable or improved clinically

Partial response Partial response requires all of the following criteria compared with the baseline scan: (1) greater than or equal to 50% decrease in the product of perpendicular diameters of the lesion on T2 or FLAIR imaging sustained for at least 4 weeks compared with baseline; (2) no new lesions, no new T2 or FLAIR abnormalities apart from those consistent with radiation effect, and no new or increased enhancement; and (3) patients should be on a corticosteroid dose that should not be greater than the dose at time of baseline scan, and should be stable or improved clinically

Minor response Minor response requires the following criteria compared with baseline: (1) a decrease of the area of non-enhancing lesion on T2 or FLAIR MR imaging between 25% and 50% compared with baseline; (2) no new lesions, no new T2 or FLAIR abnormalities apart from those consistent with radiation effect, and no new or increased enhancement; and (3) patients should be on a corticosteroid dose that should not be greater than the dose at time of baseline scan, and should be stable or improved clinically Stable disease Stable disease is present if the changes do not qualify for complete, partial, or minor response, or progression and requires: (1) stable area of non-enhancing abnormalities on T2 or FLAIR imaging; (2) no new lesions, no new T2 or FLAIR abnormalities apart from those consistent with radiation effect, and no new or increased enhancement; and (3) patients should be on a corticosteroid dose that should not be greater than the dose at time of baseline scan, and should be stable or improved clinically

Progression Progression is defined by any of the following: (1) development of new lesions or increase of enhancement (radiological evidence of malignant transformation); (2) a 25% increase of the T2 or FLAIR non-enhancing lesion on stable or increasing doses of corticosteroids compared with baseline scan or best response after initiation of therapy, not attributable to radiation effect or to comorbid events; (3) definite clinical deterioration not attributable to other causes apart from the tumour, or decrease in corticosteroid dose; or (4) failure to return for evaluation because of death or deteriorating condition, unless caused by documented non-related disorders

13.613.5 Duration of Response

Duration of overall response: The duration of overall response is measured from the time measurement criteria are met for CR or PR (whichever is first recorded) until the first date that recurrent or progressive disease is objectively documented (taking as reference for progressive disease the smallest measurements recorded since the treatment started).

The duration of overall CR is measured from the time measurement criteria are first met for CR until the first date that progressive disease is objectively documented.

Duration of stable disease: Stable disease is measured from the start of the treatment until the criteria for progression are met, taking as reference the smallest measurements recorded since the treatment started, including the baseline measurements.

13.713.6 Progression-Free Survival (PFS) and Overall Survival (OS)

PFS is defined as the duration of time from start of treatment to time of progression or death, whichever occurs first.

OS is defined as the time from the first dose of nivolumab to death due to any cause. All other participants will be censored at the last date known to be alive.

13.813.7 Response Review

For this trial where the response rate is the primary endpoint, all responses be reviewed by the Sponsor Investigator and/or designee of the study at the study's completion. Simultaneous review of the participants' files including corticosteroids usage and neurological status in conjunction with radiological images is the best approach.

13.913.8 Unblinding Procedures

Not applicable.

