13.3 Response Criteria

For the purpose of treatment decisions in this study, tumor progression will be assessed by the treating investigator using a consistent and objective assessment of tumor response based on the Response assessment in Neuro-Oncology (RANO) Criteria (see Appendix 4).³⁷ Treatment post-progression and confirmation of progression per Immunotherapy Response Assessment in Neuro-Oncology (iRANO) Criteria is permitted for patients who are clinically stable (see Appendix 5).³⁸

Response/Progression Categories (RANO criteria):

- **Complete response (CR).** All of the following criteria must be met:
 - Complete disappearance of all enhancing measurable and non-measurable disease sustained for at least 4 weeks. In the absence of a confirming scan 4 weeks later, this scan will be considered only stable disease.
 - No new lesions.
 - All measurable and non-measurable lesions must be assessed using the same techniques as baseline.
 - Patients must be on no steroids or on physiologic replacement doses only.
 - Stable or improved non-enhancing (T2/FLAIR) lesions
 - Stable or improved clinically, for clinical signs and symptoms present at baseline and recorded to be disease related

Patients with residual non-measurable disease cannot have a complete response.
The best response possible is stable disease.
- **Partial response (PR).** All of the following criteria must be met:

- Greater than or equal to 50% decrease compared to baseline in the sum of products of perpendicular diameters of all measurable enhancing lesions sustained for at least 4 weeks. In the absence of a confirming scan 4 weeks later, this scan will be considered only stable disease.
- No progression of non-measurable disease.
- No new lesions.
- All measurable and non-measurable lesions must be assessed using the same techniques as baseline.
- The steroid dose at the time of the scan evaluation should be no greater than the dose at time of baseline scan.
- Stable or improved non-enhancing (T2/FLAIR) lesions on same or lower dose of corticosteroids compared to baseline scan.
- Stable or improved, for clinical signs and symptoms present at baseline and recorded to be disease related clinically.
- Patients with non-measurable disease cannot have a partial response. The best response possible is stable disease.

- **Progressive disease (PD).** Any of the following criterion must be met:

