 - > 25% increase in sum of the products of perpendicular diameters of enhancing lesions (over best response [smallest tumor size] or baseline if no decrease) on stable or increasing doses of corticosteroids
 - Any new enhancing measurable lesion that when added to the change in initial tumor(s) exceeds a 25% increase in cross-sectional area.
 - Clear clinical deterioration not attributable to other causes apart from the tumor (e.g. seizures, medication side effects, complications of therapy, cerebrovascular events, infection, etc.). The definition of clinical deterioration is left to the discretion of the investigator but it is recommended that a decline in the Karnofsky Performance Score (KPS) from 100 or 90 to 70 or less, a decline in KPS of at least 20 from 80 or less, or a decline in KPS from any baseline to 50 or less, for at least 7 days, be considered neurologic deterioration, unless attributable to co-morbid events or changes in corticosteroid dose.
 - Failure to return for evaluation due to death or deteriorating condition
 - Classification of progressive disease may be deferred for up to three months for patients with initial radiographic findings consistent with progressive disease (criteria a and b above) as detailed below. However, if follow-up imaging after three months confirms progression or if the patient experiences significant clinical decline at any time, the date of actual progression will be back-dated to the first date that the patient met criteria for progression and such patients should discontinue further immunotherapy.

- **Stable disease (SD).** All of the following criteria must be met:
 - Does not qualify for CR, PR, or progression.
 - All measurable and non-measurable sites must be assessed using the same techniques as baseline.
 - Stable clinically.
- **Unknown response status.** Progressive disease has not been documented and one or more measurable or non-measurable lesions have not been assessed.

Table 13.1 RANO Response Criteria Summary

	CR	PR	SD	PD#
T1 + Gd	None	≥50% decrease	<50% decrease to <25% increase	≥25% increase (including new lesions)*
T2/FLAIR	Stable/Decrease	Stable/Decrease	N/A	N/A
New Lesion	None	None	None	Present (contributing to lesion size)*
Corticosteroids	None	Stable/Decreased	Stable/Decreased	Stable/Increasing
Clinical Status	Stable or Improved	Stable or Improved	Stable or Improved	Clinical decline*
Requirement for Response	All	All	All	Any*

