In addition, in uncertain cases in which acquisition of tumor histopathology by biopsy or resection is thought to be feasible, pathological assessment might be considered to clarify the cause of progressive imaging findings. If pathology confirms a predominance of recurrent tumor, the cause should be considered to be true progression. For cases where there is no evidence of a viable tumor, or where a prominence of gliosis or inflammation with restricted viable tumor is reported, the cause should be deemed consistent with treatment effect, and such patients should be classified as stable and allowed to continue therapy.

Unable to Evaluate (UE): Defined by any of the following:

- A patient's corticosteroid dosage has increased within 2 weeks of MRI assessment relative to the dose taken at the time of the previous assessment, cannot be classified as having a complete response, partial response, or stable disease and should be classified as non-evaluable at that time point. Conversely, patients who decrease corticosteroid use within 2 weeks of MRI assessment relative to the dose taken at the time of the previous assessment cannot be classified as having progressive disease and should be classified as nonevaluable.
- Radiographic changes indicative of progression are suspected due to other causes, including decreased steroid doses. Note: In contrast, if clinical deterioration occurs but is attributed to other causes, the time point response should be assessed with consideration to radiographic response and steroid use.
- Any target and/or non-target lesion present at baseline becomes unevaluable, including surgical removal of any target and/or non-target lesion. Note: PD can be determined without evaluation of all sites of disease based on the SPD for target lesions, evaluation of unequivocal progression in non-target lesions or observation of a new lesion within the available radiographic or clinical assessments.

Columbia University Medical Center
Herbert Irving Comprehensive Cancer Center
Version Date: January 30, 2024

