15.2 Size/Accrual Rate

Based on prior historical data showing an overall response rate (ORR) of 9% in recurrent high-grade gliomas (grade III and IV)³⁹, and 0% on the IDH inhibitor trial (AG-221)³ we set the null hypothesis of an ORR = 10% and the alternative hypothesis of an ORR = 30%. With one-sided $\alpha=0.05$ and $\beta=0.10$, a sample size of 33 evaluable participants will be needed to assess the preliminary efficacy of this regimen. We expect to accrue a total of 37 participants across all sites to account for a 10% of participants who may be deemed unevaluable for response.

We expect an accrual rate of 3 participants per month.

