15.4 Analysis of Primary Endpoints

Objective Response Rates

Objective response rate is defined as the proportion of patients with a reduction in tumor size while on treatment with nivolumab. Overall objective response rate is the sum of participants with either a partial response or complete response. Tumor size as measured on MRIs every 8 weeks will be used to determine response rate. The initial MRI prior to starting on study will serve as a baseline for comparison. Partial and complete responses will be based on RANO or criteria (See **Section 13.3**). This will be used to evaluate the direct therapeutic effect of nivolumab in IDH mutant gliomas previously exposed to alkylating agents. The objective response rate will be compared to the null hypothesis using an exact test. The null hypothesis is an objective response rate of 10% based on historical data in patients with recurrent high-grade gliomas. The objective response rate and a 95% confidence interval will be reported.

A central review of all scans collected during the course of the study for all enrolled patients will be completed by the Sponsor Investigator and/or designee to review and confirm response assessment

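### Table 13.3 gives a partial response when non-target disease is not evaluated, section 13.3 makes that status unknown, and no text says which rule decides the primary ORR

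*Combined protocol and SAP*

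**What the plan says.** The primary endpoint is ORR by RANO (13.1), and 15.4 refers CR and PR to RANO and section 13.3. Best overall response is assigned in 13.4.3, which says "The participant's best response assignment will depend on the achievement of both measurement and confirmation criteria" and gives Table 13.3. The table combines target lesions, non-target lesions and new lesions. Without new lesions, target CR with non-target disease not evaluated gives overall PR. The target-PR row also gives PR, and its non-target cell includes not evaluated as one of the permitted states.

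The RANO list in 13.3 sets more conditions for PR. All measurable and non-measurable lesions must be assessed, non-measurable disease must not progress, and T2/FLAIR disease must be stable or better. On steroids it says "The steroid dose at the time of the scan evaluation should be no greater than the dose at time of baseline scan". Unknown response status applies when "Progressive disease has not been documented and one or more measurable or non-measurable lesions have not been assessed". Section 15.7 lists unknown as category 9 and treats categories 4 to 9 as treatment failure.

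Section 15.4 opens its definition with "Objective response rate is defined as the proportion of patients with a reduction in tumor size while on treatment with nivolumab", then says that the overall rate counts participants with PR or CR.

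**The concern.** ORR is a count of best overall responses, so the rule that assigns them is the endpoint definition. Here two rules in the same chapter treat the same scan differently, and neither is said to override the other. In glioma the unassessed part matters, because section 13.2 classes non-enhancing T2/FLAIR disease as non-measurable and all non-measurable lesions as non-target. A PR credited under Table 13.3 can therefore rest on enhancing target lesions alone, with a required RANO component never read. In an open-label, single-arm trial judged against a fixed 10% rate, the choice between the two rules could be made after the results are known, and it could decide the primary conclusion.

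**Working it through.** **Step 1. One scan under each rule.** Take a participant whose target lesions have shrunk by at least 50%, with no new lesion, steroids not above baseline and stable clinical status, but whose T2/FLAIR disease was not evaluated.

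| Place | What it asks of non-target disease | Result |
|---|---|---|
| Table 13.3, target-PR row | may be not evaluated | PR |
| Table 13.3, target-CR row (if target lesions have disappeared) | may be not evaluated | PR |
| 13.3, RANO PR list | all lesions assessed; non-measurable disease not progressing; T2/FLAIR no worse | not PR |
| 13.3, unknown status | applies if any lesion is unassessed and no PD is documented | Unknown |
| 13.3, unable to evaluate (iRANO guidance) | applies if a baseline target or non-target lesion becomes unevaluable | UE |
| 15.7 | unknown is category 9 | failure |

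If other, fully read scans support stable disease, the strict result is SD rather than unknown. Neither counts towards ORR.

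**Step 2. The two rows against their own inputs.** The paragraphs on evaluation of target lesions, just above the table, define target CR as disappearance of all enhancing disease, measurable or not, with T2/FLAIR no worse. Target PR requires no progression of non-measurable disease and T2/FLAIR no worse. Neither can be established when non-target disease has not been evaluated, so these rows contradict the definitions that feed them.

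**Step 3. The plan's own sample size.** Inputs from 15.2: null ORR 10%, alternative 30%, one-sided alpha 0.05, beta 0.10; 15.4 specifies an exact test. With X binomial(n, p), find the smallest n for which some cut-off r has P(X ≥ r | 0.10) ≤ 0.05 and P(X ≥ r | 0.30) ≥ 0.90.

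- n = 32, r = 7: alpha 0.0358, power 0.8869 (too low).
- n = 33, r = 7: alpha 0.0417, power 0.9056 (met).
- Enrolment: 33 / (1 − 0.10) = 36.7, rounded up to 37.

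Both stated figures, 33 evaluable and 37 enrolled, are reproduced. The cut-off of 7 is derived; the plan does not state one.

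**Step 4. The effect of one disputed participant.** One-sided p = P(X ≥ x | n, 0.10).

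- n = 33: 6 responders (18.2%) p = 0.106; 7 responders (21.2%) p = 0.042.
- n = 37, if all enrolled are analysed: 7 responders p = 0.071; 8 responders p = 0.027.

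One participant is 1/33 = 3.0 percentage points. With either denominator there is a count at which one reclassified PR reverses the result.

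**Step 5. Illustration only.** Suppose the ORR by 13.3 is truly 10%, and the two rows also credit a share f of the non-responders. The credited rate is 0.10 + 0.90f. The documents give no value for f; the range is assumed.

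| f | Credited rate | P(at least 7 of 33) |
|---|---|---|
| 0 | 10.0% | 0.042 |
| 1% | 10.9% | 0.062 |
| 2% | 11.8% | 0.087 |
| 3% | 12.7% | 0.117 |
| 5% | 14.5% | 0.193 |

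**The case against.** The best defence is that the endpoint is anchored elsewhere. Sections 13.1 and 15.4 tie ORR to RANO and 13.3, and 15.4 does not cite Table 13.3. Responses are to be confirmed by an independent expert (13.1), and all scans are to be centrally reviewed (15.4). Unknown status counts as failure (15.7). MRI is scheduled every 8 weeks, so unread non-target disease may be rare. All of this stands, and it limits how often the conflict would arise. It does not remove the conflict: 13.4.3 is where best overall response is assigned, and no text tells the site or the central reader that 13.3 overrides the two rows.

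A reader might also infer that Table 13.3 drops the steroid and clinical-status criteria, since it has no such columns and the sentence above it names only measurement and confirmation. The documents do not support that. The target CR and PR definitions that feed the table already require stable or better clinical status and set a steroid condition. A participant who shrinks after a steroid increase above baseline, or who is clinically worse, is not a target PR. The iRANO guidance in 13.3 also acts on the single scan: after a recent steroid increase the participant "cannot be classified as having a complete response, partial response, or stable disease and should be classified as non-evaluable at that time point".

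**Conclusion.** The conflict is real and confined to two outcomes in Table 13.3: target CR and target PR with non-target disease not evaluated. Table 13.3 makes these PR; section 13.3, the target-lesion definitions and 15.7 do not. Because no precedence is stated, the same data can give two values of the primary ORR. That one participant can reverse the conclusion follows from the exact test and the stated design alone. How likely this is cannot be derived: the error rates for f above zero rest on an assumed range, so the documents show possible inflation of the ORR, not a known amount.

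A reader might infer from the opening sentence in 15.4 that any shrinkage counts as a response. It does not: the next sentence restricts the rate to PR and CR, and the paragraph refers to 13.3, where the 50% threshold stands. The opening sentence is loose and worth replacing, but it does not change the endpoint.

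This point does not rely on the confirmation column of Table 13.3, whose footnotes and cells may be incomplete in the text as extracted.

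**What to change.** Make three wording changes before the primary analysis.

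1. In Table 13.3, change the result of the target-CR, not-evaluated row to Unknown/UE. Split the target-PR row so that non-CR/non-PD still gives PR and not evaluated gives Unknown/UE.
2. In 13.4.3, state that a time-point CR or PR must meet all criteria of 13.3 (13.4 for participants with only non-enhancing lesions), including the steroid and clinical-status criteria already in 13.3 and in the target-lesion definitions.
3. In 15.4, replace the sentence about reduction in tumor size with: the proportion with confirmed CR or PR as best overall response per 13.3/13.4.

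The cost is a short amendment. These are the protocol's own criteria, and 33 evaluable and 37 enrolled still apply. MRI every 8 weeks, and Karnofsky status and concomitant medication at each cycle, are already scheduled (Table 12.2). The downside is that the observed ORR may be slightly lower, since scans with unread non-target disease would no longer support a response.

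### The complete response in Section 13.4 has no 4-week confirmation, and Section 15.4 does not say that only confirmed responses count in the primary ORR

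*Combined protocol and SAP*

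**What the plan says.** **Section 13.3 (RANO).** CR and PR must each hold for at least 4 weeks, and both definitions add: "In the absence of a confirming scan 4 weeks later, this scan will be considered only stable disease". The iRANO definitions, Table 13.2 and the text headed Evaluation of Target Lesions carry the same 4-week condition. Table 13.1, which only summarises RANO, has no confirmation row.

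**Section 13.4 (low-grade glioma RANO, for participants with only non-enhancing lesions).** PR needs at least a halving of the lesion on T2 or FLAIR "imaging sustained for at least 4 weeks compared with baseline". CR begins: "Complete response requires all the following criteria compared with the baseline scan: (1) Complete disappearance of the lesion on T2 or FLAIR imaging". Its other three criteria cover new lesions or enhancement, corticosteroids and clinical status. None mentions a duration or a second scan.

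**Who falls under 13.4.** Sections 6.1 and 13.2 admit participants with non-enhancing disease after approval by the lead-site PI. Their expected number is not given.

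**Section 15.4 (primary analysis).** "The objective response rate will be compared to the null hypothesis using an exact test". For the definition of CR and PR it refers to Section 13.3. It does not mention 13.4 and does not say that a response must be confirmed.

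**Table 13.3 (Section 13.4.3).** As the text reads out of the PDF, the row for PR in target lesions carries "documented at least once ≥4 wks. from baseline", and the last cell of the SD row is blank.

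**The concern.** A confirming scan keeps one-off readings out of the response rate. The primary endpoint is an open-label response rate tested against a fixed 10%, so the rule for counting a response should be the same for every participant. In 13.4 it is looser for the better category: a disappearance seen once is a response, while a halving seen once is not. Section 15.4 does not settle the matter, so the analyst would have to decide at the time of analysis whether such a CR counts. In a trial of 33 to 37 participants, a decision about one person can change the conclusion.

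**Working it through.** **1. Definitions side by side**

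| Place | CR: 4-week condition | PR: 4-week condition |
|---|---|---|
| 13.3 RANO | yes, otherwise SD | yes, otherwise SD |
| 13.3 iRANO and Table 13.2 | yes | yes |
| 13.3 Evaluation of Target Lesions | yes | yes |
| 13.4 low-grade RANO | **none** | yes |

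The 13.4 definitions are continuous prose, so the gap does not depend on how a table is laid out.

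**2. Who is affected.** ORR counts CR and PR together, and a complete disappearance is also a decrease of at least half. If a scan at least 4 weeks later still shows such a decrease and the other PR conditions hold, the participant is a 13.4 PR and counts anyway. The missing condition changes ORR only for a participant with solely non-enhancing disease whose lesion disappears on one scan and who then either loses the response or has no later scan.

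The second case can arise from the schedule. Scans are every 8 weeks (Sections 12.2 and 13.1), and the primary analysis is 6 months, about 26 weeks, after the last participant's first treatment (Section 5.1). A late enrollee who first responds at week 24 has the next scheduled scan at week 32.

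**3. The plan's own sample size.** Inputs from Section 15.2: null ORR 10%, alternative 30%, one-sided alpha 0.05, beta 0.10, and "a sample size of 33 evaluable participants will be needed to assess the preliminary efficacy of this regimen". For the exact test,

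P(X ≥ r | n, p) = Σ from k = r to n of C(n,k) p^k (1 − p)^(n − k).

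- n = 32, r = 7: alpha 0.036, power 0.887, which is short of 0.90.
- n = 33, r = 7: alpha 0.042, power 0.906. The plan's 33 is reproduced.
- Accrual: 33 / (1 − 0.10) = 36.7, rounded up to 37, as stated: "We expect to accrue a total of 37 participants across all sites to account for a 10% of participants".
- If all 37 are analysed, r = 8: alpha 0.027, power 0.905.

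**4. What one response does**

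| Responders | One-sided exact p against 10% |
|---|---|
| 6/33 | 0.106 |
| 7/33 | 0.042 |
| 7/37 | 0.071 |
| 8/37 | 0.027 |

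One response is 1/33 = 3.0 points or 1/37 = 2.7 points of ORR. At the boundary it decides the test.

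**5. Table 13.3.** With scans at 8 ± 2 weeks, the first scheduled scan is at least 6 weeks after the first dose. Read as a PR rule, the quoted phrase would be met by every scheduled scan and would add no confirmation. Read as a minimum duration for SD, it makes ordinary sense.

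**The case against.** The strongest reply is that the plan already requires confirmation. Section 13.3 states it repeatedly, Section 13.1 calls for confirmatory scans after a first response, and Section 15.4 points to 13.3. Only 13.4 CRs escape, in a subgroup admitted one by one. It is not even clear that these enter the primary ORR: Section 13.2 lists non-enhancing lesions as non-measurable, Section 13.3 caps non-measurable disease at SD, and Section 13.1.1 makes measurable disease a condition of being evaluable for response. The 13.4 CR also requires no steroids beyond physiological replacement. Section 13.1 has an independent expert confirm responses, and Sections 13.7 and 15.4 add review by the sponsor-investigator or a designee.

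Most of this stands, and it limits the size of the problem. It does not remove it. None of the reviews imposes a 4-week rule, and the doubt over whether 13.4 responses count is itself something that 15.4 should settle.

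A reader might infer more in two ways.

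- **That Table 13.3 lets single-scan PRs into the ORR.** The documents do not support this. Several cells of that column are blank, probably merged, and the table's footnotes do not appear. The phrase fits the adjacent blank SD cell. The column heading and the sentence above the table both require confirmation, and 13.3 downgrades an unconfirmed PR explicitly.
- **That the false-positive rate is inflated several-fold.** This requires adding a few points of single-scan response to the 10% null, and the documents give no such figure. Through 13.4 CRs alone, 5 points at n = 37 means 0.05 × 37 = 1.85 unsustained disappearances. With an assumed subgroup of 5 or 10, that is 37% or 18.5% of its members, which is implausible for an inactive drug. Section 15.2 also does not say whether its 10% is a confirmed-response rate.

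**Conclusion.** The point holds as a gap in the definition of the primary endpoint. The 13.4 CR lacks the 4-week condition that the 13.4 PR and every CR definition in 13.3 carry, and 15.4 states neither that responses must be confirmed nor how 13.4 responses are counted. The expected effect on ORR is probably small, and it cannot be computed because the size of the non-enhancing subgroup is not given. It matters because the decision boundary is one response wide: 6 against 7 of 33, or 7 against 8 of 37. These p-values rest on the one-sided exact binomial test against 10% and on no assumed rate of unsustained responses. The documents do not support a figure for an inflated false-positive rate. Table 13.3 is a matter for a page check and is not evidence of a second gap.

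**What to change.** 1. In Section 13.4, require the complete response to hold for at least 4 weeks, as the partial response there already must.
2. In Section 15.4, state that only confirmed CR and PR, under 13.3 or 13.4 as applicable, count in the primary ORR. Say there how a response whose confirming scan falls after the analysis cutoff is handled.
3. Check on the printed page which row of Table 13.3 carries the phrase about 4 weeks from baseline. Only if it is in the PR row, reconcile it with the confirmation rule in 13.3.

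The cost is wording. No visits are added, because Section 13.1 already schedules scans every 8 weeks after a first response. The sample size does not change: if 10% and 30% are taken as confirmed-response rates, 7 of 33 keeps alpha 0.042 and power 0.906. The downside is that ORR may be slightly lower, since a CR seen only once would score as stable disease.
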